### **7.2. Setting**

The study population will consist of HIV-1 infected adults aged  $\geq 18$  years receiving B/F/TAF who will be enrolled across participating countries (as a minimum likely to include Germany, Netherlands, United Kingdom, Ireland, France, Italy, Spain and Turkey). The start of enrolment will be determined by the availability of B/F/TAF in each of the participating countries based on national reimbursement timelines.

All treatments will be prescribed according to local treatment guidelines and/or routine clinical practice. There will be no additional diagnostic or laboratory monitoring procedures required by the study.

**7.2.1. Inclusion Criteria**

1. HIV-1 infection
2. Signed informed consent
3. Age  $\geq$  18 years old
4. Initiating treatment with B/F/TAF in accordance with the SmPC

[figure not shown]
**7.2.2. Exclusion Criteria**

1. Participation in any interventional clinical trial without prior approval from the medical monitor

### 7.3. Variables

	On-Treatment Period				B/F/TAF Discontinuation l
	Baseline/Day 1	3 Months	6, 12, 24 Months	36, 48, 60 Months*	
Informed consent	X			X**	
Demographics	X				
Weight	X		X	X	X
Date of HIV diagnosis	X				
CDC classification a	X				
New AIDS defining events		X	X	X	X
Co morbidities	X				
ART History	X				
Concomitant medications	X	X	X	X	X
Plasma HIV 1 RNA	X	X	X	X	X
CD4 cell count	X	X	X	X	X
CD4/CD8 ratio	X	X	X	X	X
Chemistry profile b	X		X	X	X
Metabolic assessments c	X		X	X	X
Urinalysis d	X		X	X	X
Reasons for ART initiation or switch to B/F/TAF	X				
AEs and SAEs		X	X	X	X
Resistance status	X		X	X	
CCI					
CCI					
CCI					
CCI					
Health Utilization Assessment			X	X	
CCI					

- a Selik RM, et al. Morbidity and Mortality Weekly Report (MMWR). Revised Surveillance Case Definition for HIV Infection United States 2014. Centers for Disease Control and Prevention, 2014.  
 CDC: Centers for Disease Control and Prevention
- b Chemistry profile: AST, ALT, Total/direct bilirubin, albumin, serum glucose, serum phosphate, serum creatinine.
- c Metabolic assessments: Lipid panel (Total cholesterol, HDL, LDL, triglycerides).
- d To include dipstick test (glucose, leukocytes, protein) and urine albumin/creatinine ratio (UACR), urine protein/creatinine ratio (UPCR).

l The evaluations should be done at the time of B/F/TAF discontinuation visit. After the B/F/TAF discontinuation visit, the subject should follow the same schedule of clinical routine evaluations, but only record data listed in this column until study completion.

Note: Patients who discontinue B/F/TAF in the extension phase are required to discontinue the study with no further follow up.

\* Only applicable for patients consenting to the extended patient follow up in Germany and France

\*\* Patients who are willing to participate in the extension phase could either re-consent onsite during 24M visit or remotely, in case the 24M visit was completed prior receiving the protocol amendment approval by country regulatory bodies.

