## 6. RESEARCH QUESTIONS AND OBJECTIVES

This non-interventional cohort study will evaluate the effectiveness, safety, adherence, resource utilization and PROs of B/F/TAF use in routine clinical care.

The primary objective of this study is:

- To evaluate HIV-1 RNA suppression, defined as HIV-1 RNA < 50 copies/mL, at 12 months after initiating or switching to B/F/TAF

The secondary objectives of this study are:

- To evaluate HIV-1 RNA suppression (<50 copies/mL) at Months 3, 6, and 24 for all patients after initiating or switching to B/F/TAF
- To evaluate changes in cluster determinant 4 (CD4) cell count and CD4/cluster determinant 8 (CD8) ratio at Months 3, 6, 12, and 24 for all patients after initiating or switching to B/F/TAF
- To assess rates of adverse events (AEs) and serious adverse events (SAEs)
- To evaluate the long-term effectiveness and safety of B/F/TAF in an extension phase through Month 60 in a subgroup of patients recruited in Germany and France:

To evaluate HIV-1 RNA suppression (< 50 copies/mL) at Months 36, 48, and 60 after initiating or switching to B/F/TAF

To evaluate changes in CD4 cell count and CD4/CD8 ratio at Months 36, 48, and 60 after initiating or switching to B/F/TAF

CCI [REDACTED]

- [REDACTED]
- [REDACTED]
- [REDACTED]
- [REDACTED]
- [REDACTED]

CCU [REDACTED]

[REDACTED]

[REDACTED]

The above parameters may be evaluated in various subgroups, e.g., ART-naive patients versus ART-experienced patients, by baseline viral load  $\geq$  or  $<$  100,000 copies/mL, age, presence of specific comorbidities, gender, as well as comparing between participating countries.

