#### **7.1.1. Early Study Drug Discontinuation**

In case of B/F/TAF discontinuation, the date of discontinuation, reasons for discontinuation (eg, patient choice, adverse reaction, lack of efficacy) and patients' new ART will be collected. The patient will remain in the study and will be followed-up with the new ART until premature end of documentation (e.g., due to lost to follow-up) or until reaching the defined end of the study (24 months after enrollment). If the patient has subsequent changes in therapy, all ARV changes will be recorded until the patient completes the study.

For the extension phase of the study, applicable for patients in Germany and France: In case of B/F/TAF discontinuation in the extension phase, patients must be discontinued from the study with no further follow-up data being collected.

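### The discontinuation column in section 7.3 omits resistance status and health utilization, so neither has a scheduled record at or after the stop visit, and the gap is related to outcome

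*Protocol*

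**What the plan says.** The schedule in Protocol section 7.3 has four visit columns and a fifth for B/F/TAF discontinuation. The row "Resistance status" is marked at baseline, at Months 6, 12 and 24, and at Months 36, 48 and 60. The row "Health Utilization Assessment" is marked at the same visits except baseline. Neither is marked at Month 3 or in the discontinuation column.

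The footnote to that column governs both the stop visit and the time after it. For the visit: "The evaluations should be done at the time of B/F/TAF discontinuation visit". For later visits, the patient stays on the routine schedule, "but only record data listed in this column until study completion".

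Section 7.1.1 expects stopping to be linked to outcome in part. It collects the "reasons for discontinuation (eg, patient choice, adverse reaction, lack of efficacy"). For the first 24 months it also keeps these patients under observation: "The patient will remain in the study and will be followed-up with the new ART until premature end of documentation". In the extension the rule differs: "Patients who discontinue B/F/TAF in the extension phase are required to discontinue the study with no further follow up".

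Section 6 makes resource utilization part of the study's purpose: "This non-interventional cohort study will evaluate the effectiveness, safety, adherence, resource utilization and PROs of B/F/TAF use in routine clinical care".

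**The concern.** Whether the two items are recorded depends on whether the patient is still on B/F/TAF, and some patients come off it because it failed or was not tolerated. When failure leads to a stop, a genotype ordered in routine care because of that failure is likely to become available at the stop visit or later, where it has no scheduled field. Resource use in the run-up to a stop for an adverse reaction belongs to time on B/F/TAF, yet the visit that closes that period does not ask for it.

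Summaries of resistance and utilization built from the scheduled fields would therefore under-represent the periods around failure and intolerance. The likely direction is towards less resistance and, if use rises before a stop, towards lower utilization. The patients remain in follow-up to Month 24, so for those who stop by then the gap comes from the recording rule and not from loss of contact.

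**Working it through.** No sample size, power or error rate is involved, and the plan has no figure to reproduce. The check is a cell-by-cell reading of the section 7.3 table against its footnote and section 7.1.1.

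**Step 1. Which follow-up items carry over to the discontinuation column?** The count takes visible rows marked in at least one scheduled follow-up column and leaves out informed consent, which is marked there only for re-consent.

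| Item | Months 6/12/24 | Months 36/48/60 | Discontinuation |
|---|---|---|---|
| Weight; new AIDS-defining events; concomitant medications; HIV-1 RNA; CD4 count; CD4/CD8 ratio; chemistry; metabolic; urinalysis; AEs and SAEs (10 rows) | marked | marked | marked |
| Resistance status | marked | marked | blank |
| Health utilization | marked | marked | blank |

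Ten of 12 rows carry over, and these are the only two that do not. The redacted rows cannot be assessed.

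**Step 2. What has no scheduled record, by time of stopping?** For utilization this assumes that each assessment covers the time since the previous one; the recall period is not visible.

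| Stop | Last scheduled record of utilization | On-treatment utilization not covered | Post-baseline resistance record |
|---|---|---|---|
| Before Month 6 | none | up to 6 months | none |
| Months 6 to 12 | Month 6 | up to 12 − 6 = 6 months | Month 6 only |
| Months 12 to 24 | Month 12 | up to 24 − 12 = 12 months | to Month 12 |
| Extension | Month 24, 36 or 48 | up to 12 months | to that same visit |

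**Step 3. Is there a later chance to record?** For a stop in the first 24 months, follow-up continues on the new regimen, but the footnote excludes both items. In the extension, stopping ends participation, so the stop visit is the last opportunity and the column omits both items there too.

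**Step 4. How many patients?** The protocol gives no B/F/TAF discontinuation rate. The 35% at Month 60 in section 7.5 is cumulative drop-out from the study and cannot stand in for one. As a scale only, each percentage point of the planned 1500 who stop is 0.01 × 1500 = 15 patients. Not all of them would have a genotype.

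**The case against.** The strongest reply is that the signal of failure or harm is still captured. HIV-1 RNA, CD4 count and new AIDS-defining events stay in the discontinuation column. The reason for stopping and all later antiretroviral changes are recorded (section 7.1.1). Lack of effect is a special situation report (section 9.3.5). In-patient hospitalization makes an event an SAE (section 9.3.3), and section 9.1 continues SAE collection after B/F/TAF is stopped. Unscheduled visits collect whatever local practice provides (section 7.3.1), which may admit a genotype. All of this stands and makes the loss partial. It does not close the gap: viral load shows viraemia but not mutations, SAEs cover admissions but not other resource use, and section 7.3.1 requires neither item.

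A second reply is that utilization should be limited to time on drug. The aim in section 6 concerns B/F/TAF use, and the visits are headed as on-treatment. This is a defensible scope for the period after a switch. It does not explain leaving the item off the stop visit, which closes an on-treatment interval.

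A reader might go further and infer that both items are lost altogether in exactly the patients who fail or do not tolerate treatment, so that a finding of no emergent resistance would be produced by the schedule. The documents do not support that. Records from earlier on-treatment visits are kept, patients who rebound but stay on B/F/TAF keep both items, and some patients stop by choice. Resistance is not named in the visible objectives, which are partly redacted, nor in the analyses of section 7.7. Conflict with a stated aim is therefore documented only for resource utilization.

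**Conclusion.** The concern holds in a limited form. As written, section 7.3 provides no scheduled record for a routine-care genotype obtained at or after stopping for virological failure, or for resource use on B/F/TAF between the last scheduled visit and the stop. Patients who stop before Month 6 have no scheduled post-baseline record of either item. The omission is selective, since 10 of 12 visible follow-up items carry over and no reason is given for the other two, and stopping is partly driven by outcome.

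Per patient, the uncovered on-treatment interval for utilization is up to 6 months for a stop in the first year and up to 12 months later, given the recall assumption above. The number of patients and the size of any bias in a resistance or utilization summary cannot be derived from the protocol; a percentage would rest on an assumed discontinuation or resistance rate. The change is worth making because it reduces outcome-related missing data at little cost. The primary analysis is not affected.

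**What to change.** In the section 7.3 schedule:

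- Mark resistance status in the discontinuation column, defined as any genotype already done in routine care. Record it at the stop visit and, for patients who stop in the first 24 months, through follow-up to Month 24. In the extension it applies at the stop visit only.
- Mark the Health Utilization Assessment at the discontinuation visit, to cover the on-treatment interval since the last scheduled assessment. If use after the switch is left out, which is optional, the footnote should say that this item applies to the stop visit only.

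No test or visit is added, so the commitments in sections 7.2 and 7.4 to no extra monitoring, visits or procedures are respected. The cost is two cells, a footnote edit, an eCRF update and a little extra data entry. If the utilization item is patient-completed, which cannot be determined because the neighbouring rows and section 7.3.2 are redacted, there may also be one more questionnaire at the stop visit.

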### 7.3.1. **Unscheduled Visit Assessments**

For patients requiring follow up outside of the normal routine clinic visits, the variables collected will be according to local medical practice.

### 7.3.2. **Patient-Reported Outcomes**

CCI [Redacted]

[Redacted]

[Redacted]

[Redacted]

[Redacted]

[Redacted]

[Redacted]

CCI [Redacted]

[Redacted]

[Redacted]

[Redacted]

#### **7.4. Data Sources**

Data will be collected from participating countries (as a minimum, likely to include Germany, Netherlands, United Kingdom, Ireland, France, Italy, Spain, and Turkey).

Each investigator at the participating sites will offer the study to potentially eligible patients, for whom, the independent decision to prescribe B/F/TAF has been made. The decision to prescribe B/F/TAF should be made by a patient's primary HIV care provider and should not be related to study entry. Potential participants will be asked to sign an ICF for the collection of retrospective and prospective data. Patients will not have to attend any additional visits or undergo any procedures above their standard of care.

Data collection will be performed by manual entry of data from the patient's medical file and questionnaires to a computer based eCRF. No patient initials will be included and only anonymized data will be entered.

#### **7.5. Study Size**

At least 1500 patients starting treatment with B/F/TAF (to include both ART-naive and ART-experienced patients) are planned to be enrolled into the study.

A sample size of 1500 patients will be appropriate to detect a proportion of HIV RNA suppression (< 50 copies/mL) of at least 90% with a power of 80% (Score z test: target proportion 90%, smallest detectable proportion 92.10%).

Additionally, assuming there are 30% of patients over age 50 years, then with 1050 patients < 50 years and 450 patients 50 years or older, there is more than 90% power to detect a difference in HIV RNA response rate between the age groups of at least 7%, assuming a 90% response rate in older patient (versus 83% in younger patients) and a two-sided alpha of 0.05 and a continuity corrected test of two proportions.

With a target of at least 200 patients per country, there is 80% power to determine a 7% difference in HIV RNA response rates between any country and the remaining countries, assuming a 90% response rate in the overall countries. In addition, assuming a 90% response rate in one country with 200 patients, there is more than 80% power to determine an 11% difference in HIV RNA response rates compared to any country including the same sample size.

The study will not have strict enrollment goals for specific strata of patient types. However, the protocol team will monitor enrollment into specific strata of interest (e.g., age > 50 years, treatment naive) and may close enrollment to a stratum in order to preserve statistical power to evaluate subgroups of interest.

Patients recruited in Germany, France and Canada (protocol ID: GS-CA-380-4574) will be included in the extension phase HIV RNA analysis. From the existing cohort of patients, a subsample of 400 patients will be appropriate to detect a proportion of HIV RNA suppression of at least 70% with a power of 80% (Score z test: target proportion 70%, smallest detectable

proportion 76.4%). A cumulative drop-out rate of 35% at Month 60 was applied to derive the projected Month 60 sample size.

## **7.6. Data Management**

After finalization and approval of the protocol, an electronic case report form (eCRF) will be built in a commercial electronic data capture (EDC) system to collect the data listed in the Variables section (7.3). Personal identifying data such as names, health record identifiers, and social security numbers will not be collected.

Site users will receive a unique username and password from the EDC system administrator following completion of the EDC system training. Receipt of username, password and successful completion of EDC training, will allow site to enter data into the EDC system. Investigators will electronically sign the eCRFs to confirm responsibility for the data following completion of data entry and data quality activities. Study data will be stored on secure network drives with access restricted to authorized personnel only.

After reviewing the questionnaires for completeness, the questionnaires will be returned to the Contract Research Organisation for data entry into the EDC system.

## **7.7. Data Analysis**

For categorical variables, numbers and percentages of patients will be reported including the according 95% confidence intervals.

For continuous variables, mean, SD, minimum, first and third quartile (Q1, Q3), median, maximum and 95% confidence intervals will be calculated, together with the total number of observations and the number of missing values.

Descriptive statistics will summarize demographics and baseline characteristics (including the type of regimen at enrolment). Once data is available from more than one country, descriptive analyses by country will be done to determine if patient heterogeneity exists across countries and sites.

The questionnaires scores will be calculated according to the algorithms elaborated for these questionnaires.

Visit windows will be defined in the Statistical Analysis Plan (SAP) to group data in order to generate descriptive statistics across time to assess potential trends in PRO questionnaires, safety data, or CD4. P-values and/or confidence intervals (95% two-sided) will be calculated when considered relevant.

Following descriptive analysis, a multiple imputation approach will be used to carry out multivariate analyses in case the assumptions of missing at random (MAR) are met. If this assumption doesn't hold, a complete case (subjects with all variables present) or regression approach may be used dependent on the results of a sensitivity analysis. Patterns of missing data

will be determined using the methodology outlined by Rubin {Rubin 1976}. Imputation methods will be used to account for missing values in the dataset adhering to current European Network of Centres for Pharmacoepidemiology and Pharmacovigilance (ENCePP) guidelines {European Medicines Agency 2010}.

Multivariate logistic regression models will be used to model binary outcome variables (HIV-1 RNA suppression, change in CD4 cell count category (e.g. CD4 > 500 at week 48), HIV RNA suppression, adherence and persistence of B/F/TAF).

Multivariate Poisson regression models will be used to model questionnaires scores (CCI ) and rates of adverse drug reactions (ADRs) and serious adverse drug reactions (SADRs), adjusted for confounding.

Multivariate analyses will be also conducted to compare treatment-naive and non-naive treatment groups. In order to maximize homogeneity between groups and reduce the impact of treatment-selection bias, an inverse probability of treatment weighted approach will be applied (Rosenbaum and Rubin 1983, Thoemmes and Ong 2016, {Austin 2011b} {Austin 2011a}). Demographics and baseline measures would be potential confounders/effect modifiers for multivariate analyses. Confounders/effect modifiers and respective adjustments will be addressed in the SAP. For multivariate analyses, significantly skewed data will be transformed using the fractional polynomial approach (Royston et al. 1999). Longitudinal analysis will be done using mixed models. Further details of the data analysis will be provided in the SAP.

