## **7.9. Limitations of the Research Methods**

This study has the characteristic limitations of observational studies, for example selection bias, information bias and missing values.

In order to reduce selection bias, patient's eligibility criteria have been well defined. However, this is not a type of bias easy to prevent or measure. A selection bias introduced by the choice of sites that contribute patient data cannot totally be avoided. However, a selection of sites in multiple countries will help to reduce this kind of bias.

This study is a non-comparative, non-interventional study, and as a result, confounding by indication (ie, confounding indicated by study drug) should be a minimal issue in the absence of a comparator. Multivariate analyses will aim to minimize potential confounding by indication by including disease assessment and according details of treatment in the analyses.

Information bias can be prevented by using standard measurement instruments, like eCRF and appropriate training of personnel entering the data. Appropriate training of personnel entering data is also important to avoid missing values when checking the patient' medical records.

As documentation of the study variables is not obligatory, the extent to which missing data occurs is unpredictable. Patterns of missing data will be determined using the methodology outlined by Rubin et al {Rubin 1976}. Here, it has to be determined if the "MAR" criterion is fulfilled. If the assumptions of MAR or missing completely at random (MCAR) are met, then a multiple imputation approach will be used. If this assumption doesn't hold, a full case or regression approach may be used.

Multiple imputation by chained equations (MICE) also referred to as sequential regression multiple imputation, is a validated statistical method for the handling of missing data {Azur 2011}. Using MICE, missing values are imputed based on the observed values for a given individual and the relationships within the data for other participants.

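### Multiple imputation depends on an MAR check that observed data cannot settle, and the fallback does not address data missing not at random

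*Protocol*

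**What the plan says.** Section 7.7 of the protocol sets the rule in two steps. First, "a multiple imputation approach will be used to carry out multivariate analyses in case the assumptions of missing at random (MAR) are met". Second, if that assumption fails, "a complete case (subjects with all variables present) or regression approach may be used dependent on the results of a sensitivity analysis". The same paragraph then says, with no condition attached, "Imputation methods will be used to account for missing values in the dataset".

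Section 7.9 repeats the rule with differences. It says that "Patterns of missing data will be determined using the methodology outlined by Rubin et al" and that fulfilment of the MAR criterion has to be established. It allows imputation if either MAR or MCAR is met, and then adds: "If this assumption doesn't hold, a full case or regression approach may be used". It does not mention the sensitivity analysis that 7.7 uses to choose the fallback.

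Neither section says what would count as MAR being met, what the regression approach is, or which method would apply if missingness depends on the unseen values. The multivariate models listed in 7.7 include a logistic model for HIV-1 RNA suppression, the variable of the primary objective. Section 7.9 also concedes that sites need not document every variable and that the amount of missing data cannot be foreseen.

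**The concern.** Two features of the rule are wrong as written.

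1. **The gate cannot be operated.** Whether data are MAR or MNAR depends on the values that were not observed. Patterns of missingness can give evidence against MCAR. They cannot show that MAR holds against MNAR. The decision would in practice be a judgement made after the descriptive results are known.
2. **The fallback does not fit its trigger.** If MAR is judged to fail, the remaining concern is MNAR. Complete-case analysis does not model MNAR, and neither does an ordinary regression on observed records. Read literally, 7.9 turns to complete cases only once MCAR has also been excluded, and MCAR is the condition under which complete cases are unbiased for every quantity.

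The stake is the credibility of the modelled results, above all the suppression model. Patients without a viral-load result may plausibly be those out of care or failing treatment. Nothing in the rule requires a result that shows how far conclusions would move if that were so.

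**Working it through.** **Side-by-side reading**

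| Situation as judged | Section 7.7 | Section 7.9 |
|---|---|---|
| MCAR | not mentioned | multiple imputation |
| MAR | multiple imputation | multiple imputation |
| Neither | complete case or regression, optional, guided by a sensitivity analysis | full case or regression, optional |
| Any | imputation will be used (unconditional sentence) | no such sentence |

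The last row conflicts with the complete-case branch unless the reader silently carries the MAR condition forward.

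**Scale for comparison.** Section 7.5 sizes the study on 90% against 92.10% with N = 1500 and 80% power. One-sample score z test, two-sided alpha 0.05 (alpha is not stated for this test):

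- power = Φ[(0.021 − 1.96 × √(0.9 × 0.1/1500)) / √(0.921 × 0.079/1500)] = Φ[(0.021 − 0.01518)/0.00696] = 79.8%, which reproduces the plan.
- One-sided alpha 0.05 gives 88.2%, which does not.

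The yardstick is therefore 92.1 − 90 = 2.1 points.

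**Illustration 1: suppression proportion, simple form.** Overstatement = share missing × (suppression in the observed − suppression in the missing). Both inputs are assumed:

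- 0.08 × 10 = 0.8 points
- 0.20 × 30 = 6.0 points

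**Illustration 2: complete cases against imputation for that proportion.** Assume that 30% of patients are in a risk group with 78% suppressed and the rest have 95%. True overall: 0.3 × 0.78 + 0.7 × 0.95 = 89.9%. Among suppressed patients, 40% of the risk group and 10% of the others are missing. Under MNAR, the odds of being missing are multiplied by OR for those not suppressed. Imputation conditions on risk group.

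MAR case worked through: complete cases = (0.3 × 0.6 × 0.78 + 0.7 × 0.9 × 0.95)/(0.3 × 0.6 + 0.7 × 0.9) = 0.7389/0.81 = 91.2%, a bias of +1.3 points. Imputation returns 89.9%.

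| Mechanism | Missing | Complete-case bias (points) | Imputation bias (points) |
|---|---|---|---|
| MAR | 19% | +1.3 | 0.0 |
| MNAR, OR 1.5 | 20% | +2.2 | +1.1 |
| MNAR, OR 2 | 20% | +2.9 | +1.9 |
| MNAR, OR 3 | 21% | +4.0 | +3.1 |
| MNAR, OR 5 | 22% | +5.2 | +4.6 |
| Outcome only, OR 3 (20% missing among suppressed in both groups) | 22% | +2.7 | +2.5 |

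Neither method removes MNAR bias, so switching from imputation to complete cases is no remedy.

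**Illustration 3: logistic coefficients, which the rule governs.** Simulation of 200,000 patients with one stochastic imputation. True intercept and slopes are 2.5, −0.7, −0.3.

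| Mechanism | Complete cases | Imputation |
|---|---|---|
| First covariate missing, depending on itself | 2.498, −0.682, −0.290 | 2.235, −0.676, −0.330 |
| First covariate missing, depending on outcome and the other covariate (MAR) | 2.938, −0.705, +0.146 | 2.500, −0.701, −0.295 |
| Outcome missing, depending on itself | 2.821, −0.695, −0.302 | 2.794, −0.704, −0.314 |
| Outcome missing, depending on itself and on its interaction with the first covariate | 2.863, −0.334, −0.285 | 2.828, −0.389, −0.297 |

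Complete cases are closer overall in the first row. Imputation is right in the second. Slopes are close under both in the third, and the first slope is badly biased under both in the fourth.

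**Precision.** If 10 covariates were each 5% missing independently (assumed), 0.95^10 = 0.599 of patients would be complete, about 898 of 1500.

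**The case against.** The strongest defence is that the wording is permissive and incomplete by design. The fallback is complete case or regression, it only may be used, and in 7.7 it depends on a sensitivity analysis whose specification belongs to the SAP, as do further analysis details generally. The study is non-comparative and its primary objective is descriptive. The checklist in Appendix 1 answers No on whether hypotheses to be tested are stated, so the 2.1 points come from a power statement and are not a decision margin. All of this is fair, and it limits how much weight the numbers can bear.

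Three stronger readings are tempting, and the documents do not support them:

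- A reader might infer that complete cases always need a stronger assumption than imputation. That is not so in regression. Complete cases are valid when missingness is independent of the outcome given the covariates, even if a covariate is MNAR, and the first simulation row shows imputation doing worse there.
- A reader might infer that bias is largest exactly when the rule is triggered. Because MAR is untestable, the trigger need not coincide with true MNAR, and the coefficient results are mixed.
- A reader might infer that the primary Month 12 proportion will rest on patients with a result. The conditional rule names only the multivariate analyses. The unconditional imputation sentence, or the SAP, may cover the descriptive proportion.

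What the defence does not answer is the gate itself. The protocol fixes that, so an SAP that follows the text inherits a condition that cannot be verified and a fallback that does not address its failure.

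**Conclusion.** The point stands as a rule that is wrong as written, confined to the multivariate analyses. Sections 7.7 and 7.9 make imputation depend on a condition that the data cannot establish, send the analysis to methods that do not address MNAR when the condition is judged to fail, and contradict the unconditional imputation sentence in 7.7.

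The size is not determined by the documents. Under the assumptions shown, the distortion of a suppression proportion ranges from well below the 2.1-point design difference to nearly three times it (6.0/2.1 = 2.9). That is an illustration for the proportion only. It does not estimate bias in the planned models, where either method may be the better one depending on the mechanism. This uncertainty is the reason to require MNAR sensitivity analyses whatever the observed patterns show.

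**What to change.** In sections 7.7 and 7.9, and in the SAP to match:

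1. Delete the determination of MAR as a gate. Describe missingness patterns for information only.
2. State that multiple imputation by chained equations under MAR is the main approach for the multivariate models, including the HIV-1 RNA suppression model. This also brings the unconditional imputation sentence into line.
3. Always report MNAR sensitivity analyses: delta-adjusted imputation with a tipping point and, for the suppression outcome, an analysis that counts missing as not suppressed.
4. Keep complete-case results as a supporting table, with comment where they differ from the imputed results, since complete cases can be valid for some covariate mechanisms. Drop the undefined regression approach.

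The cost is protocol and SAP wording and some extra programming, with no new data. The downside is a worst-case bound that will look less favourable than the main result.
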